6.4 STUDY INTERVENTION COMPLIANCE

Compliance with study drug will be recorded on a Case Report Form (CRF) by research or other designated staff at each participating site. This study will utilize electronic CRFs (eCRFs). As the medication is injected subcutaneously in an observed situation on a monthly basis, we can ensure intervention compliance.

6.5 CONCOMITANT THERAPY

For this protocol, a prescription medication is defined as a medication that can be prescribed only by a properly authorized/licensed clinician. Medications to be reported in the eCRF are concomitant prescription medications, over the counter medications, and supplements.

6.5.1 PROHIBITED TREATMENTS

No dietary changes, dilations, changes in baseline PPI medication dose, changes in inhaled or intranasal steroid doses, or administration or oral, topical/swallowed, or systemic steroids will be allowed during the study period (from consent through the end of treatment period). Esophageal dilation at the screening or month 3 endoscopy will result in study exit. However, dilation may be performed during or after the month 6 endoscopy, if clinically indicated.

If a subject has severe persistent or recurrent symptoms, or experiences a food impaction during the treatment period, rescue medications and procedures to treat EoE are allowed for clinical purposes. The sponsor will not supply rescue medications, and these would need to be prescribed as clinically indicated by the subject's physician. However, if such medications or treatments are required, the participant would be considered a treatment failure and would exit the study. If this happens, and at the discretion of the site-Investigator or sponsor-investigator it is safe and feasible to do so, the subject should return for an early termination visit.

Although the use of rescue medications is allowable at any time during the study, if safe and feasible to do so the use of rescue medications should be delayed until either the 3-month or 6-month assessments are completed. Rescue medications or treatments administered after the month 6 EGD will not result in study exit. The date and time of rescue medication administration as well as the name and dosage regimen of the rescue medication must be recorded.

7 STUDY INTERVENTION DISCONTINUATION AND PARTICIPANT DISCONTINUATION/WITHDRAWAL

7.1 DISCONTINUATION OF STUDY INTERVENTION

Subjects may choose to withdraw from participation in the study at any time upon their request without penalty. Additionally, the investigator and sponsor may withdraw a subject from the study in the event of an intercurrent illness, adverse event (AE), treatment failure, protocol violation, cure, and for administrative or other reasons. Discontinuation from study treatment does NOT automatically lead to a complete withdrawal from the study. Subjects discontinuing from study treatment are strongly encouraged to complete early termination procedures and safety follow up.

Investigators should withdraw study treatment from subjects if any of the following occur:

- Pregnancy
- Lost to follow up
- Hypersensitivity / systemic allergic reaction to the study treatment requiring administration of epinephrine
- The subject meets an exclusion criterion (either newly developed or not previously recognized) that precludes further study participation

- Worsening symptoms or disease progression that, in the opinion of the investigator, requires either esophageal dilation or EoE treatment with either topical or systemic steroids during the treatment period
- Any adverse event that, in the opinion of the investigator, precludes safe continuation with the study protocol and study dosing
- Significant study intervention non-compliance, in the opinion of the investigator
- Any condition that, in the judgment of the site-PI or Sponsor, would compromise the ability of the patient to comply with the study protocol or complete the study

Before deciding to discontinue study treatment, the site-PIs should consult the Sponsor-Investigator and study medical monitor, regardless of the reason for discontinuation. Subjects who withdraw and have received at least 1 dose of study drug should return to complete the early termination visit.

The reason for participant discontinuation or withdrawal from the study will be recorded on the eCRF. Subjects who sign the informed consent form and are randomized but do not receive the study intervention may be replaced. Subjects who sign the informed consent form, and are randomized and receive the study intervention, and subsequently withdraw, or are withdrawn or discontinued from the study, will also be replaced such that the goal enrollment at the end of the study can be achieved.

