8.4 VISIT MONTHS 3, 6 AND EARLY TERMINATION

During visit months 3, 6, and early termination the following will be completed:

- 1) Endoscopy with biopsy and EoE Endoscopic Reference Score (EREFS)
- 2) EEsAI
- 3) Patient Global EoE Assessment
- 4) Patient Global Impression of Change (PGIC)
- 5) Patient Global Impression of Severity (PGIS)
- 6) VAS (Visual Analog Scale) Assessment; if applicable for subjects with known allergic diseases
- 7) CBC with differential
- 8) Serum/anti-IL 5 antibodies
- 9) Vital signs
- 10) Physical Exam
- 11) Urine pregnancy test
- 12) Concomitant medication review
- 13) Administration of study intervention (see section 6 for details, 3-month visit only)***
- 14) Adverse event review and evaluation
- 15) 48-hour adverse event review and evaluation (3-month visit only)***
- 16) Straumann Dysphagia Index (SDI)
- 17) Completion of CRFs

*** No study intervention is given at the month 6 visit or early termination visit, therefore no 48-hour phone call is required for these visits.

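### Patients rescued before month 3 exit as treatment failures, are not asked for a month-3 EEsAI, and so leave the primary comparison

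*Combined protocol and SAP*

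**What the plan says.** **Rescue.** Section 6.5.1 allows rescue treatment for severe persistent or recurrent symptoms or a food impaction, but then "the participant would be considered a treatment failure and would exit the study". Where safe and feasible, "the use of rescue medications should be delayed until either the 3-month or 6-month assessments are completed". The section also requires that "The date and time of rescue medication administration as well as the name and dosage regimen of the rescue medication must be recorded".

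**Stopping drug.** Section 7.1 states "Discontinuation from study treatment does NOT automatically lead to a complete withdrawal from the study". The next sentence reads "Subjects discontinuing from study treatment are strongly encouraged to complete early termination procedures and safety follow up", and later "Subjects who withdraw and have received at least 1 dose of study drug should return to complete the early termination visit". Dosed patients who leave "will also be replaced such that the goal enrollment at the end of the study can be achieved".

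**Visits.** Section 8.4 (Visit Months 3, 6 and Early Termination) opens "During visit months 3, 6, and early termination the following will be completed" and gives one list for all three visits, including EEsAI and endoscopy. The early termination visit takes place at exit. After it, section 8.5 plans only a 30-day call about adverse events.

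**Analysis.** Section 9.3 defines the modified ITT set as dosed patients who have 3-month results for both EEsAI and endoscopy. Section 9.4.1 leaves patients with no outcome data out of the primary analyses. Last value carried forward (9.3) and assignment to failure and then to success (9.4.1) are sensitivity analyses. The primary test is an ANCOVA on change in EEsAI with baseline EEsAI as the main covariate (9.4.2).

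**The concern.** Rescue before month 3 is an outcome of treatment: the patient did badly enough to need something else. The protocol recognises this by calling the patient a failure, but that label has no role in the primary analysis. Followed as written, the rules remove such patients from the randomized comparison on the primary endpoint. Section 9.3 names no other efficacy set, so they also leave the remission and response proportions instead of counting as non-responders. Replacement restores the headcount but not the comparison of the groups as randomized. A month-3 score that was never requested cannot be recovered later, so the trial could not afterwards show how much the exclusion mattered.

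**Working it through.** **Step 1: follow a patient rescued at, say, week 7.**
- 6.5.1: treatment failure, exits.
- 6.5.1, 7.1 and schedule footnote 6: early termination visit, with EEsAI and endoscopy at the time of exit.
- 8.5: one adverse-event call 30 days later. No EEsAI is requested at the month-3 date.
- 9.3 and 9.4.1: no 3-month EEsAI or endoscopy, so not in the primary set. No rule counts the exit visit as 3-month data.
- 9.3: the last EEsAI returns through carry-forward, as a sensitivity analysis only.

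**Step 2: follow a patient who stops drug without rescue.** Section 7.1 does not equate stopping with withdrawal, and the month-3 list in 8.4 has no dosing condition. Against that, 7.1 points the patient to early termination procedures, and 9.4.2 describes the monthly EEsAI as done when patients attend for their injection. Sites could read this either way.

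**Step 3: reproduce the plan's figure.** Inputs from 9.2 and 9.4.1: difference 17 (32 versus 15), SD 20, two-sided α 0.05, power 0.90.

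n per group = 2 × (1.960 + 1.282)² × 20² / 17² = 29.1, rounded up to 30, as stated.

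With a 20% loss, 36 × 0.8 = 28.8 per group remain, and power for 17 points is 0.897 (normal approximation) or 0.887 (t). Lost numbers are therefore not the main issue; selection is.

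**Step 4: illustrate the selection.** Assumptions not in the documents: an equal share e exits each arm before month 3, the completer difference is 17, and the drug effect among exiters is d.

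All-dosed difference = (1 − e) × 17 + e × d

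| Exits per arm | d = 0 | d = 8.5 | d = 17 |
|---|---|---|---|
| 10% | 0.9 × 17 = 15.3 | 15.3 + 0.85 = 16.15 | 17.0 |
| 20% | 0.8 × 17 = 13.6 | 13.6 + 1.7 = 15.3 | 17.0 |

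**Step 5: unequal exits.** Suppose exiters do not change at all.
- 5% exit on active and 15% on placebo: 0.95 × 32 − 0.85 × 15 = 17.65.
- 15% on active and 5% on placebo: 0.85 × 32 − 0.95 × 15 = 12.95.

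If exiters in both arms instead improve by 15, the same two cases give 0.95 × 32 + 0.05 × 15 − 15 = 16.15 and 0.85 × 32 + 0.15 × 15 − 15 = 14.45. Even the direction depends on inputs the documents do not supply.

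**Step 6: power if everyone is kept.** Take 36 per arm, two-sided 0.05, normal approximation, and exiters unchanged in both arms. Mixing adds e(1 − e)m² to each arm's variance, with m = 32 or 15.
- e = 0.1: arm SDs √(400 + 0.09 × 32²) = 22.18 and √(400 + 0.09 × 15²) = 20.50, pooled 21.4. Power for 15.3 points is 0.86, or 0.90 at SD 20.
- e = 0.2: arm SDs √(400 + 0.16 × 32²) = 23.75 and √(400 + 0.16 × 15²) = 20.88, pooled 22.4. Power for 13.6 points is 0.73, or 0.82 at SD 20.

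**The case against.** The plan is open about the exclusion and already softens it. Rescue is to be held until an assessment visit where that is safe. The early termination visit collects the month-3 efficacy measures, and carry-forward expressly covers patients who terminate, so an exit EEsAI re-enters a pre-specified comparison. A post-rescue month-3 score may also reflect steroids or dilation: section 2.1 notes that dilation can relieve symptoms while eosinophilia persists.

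Much of this stands, and it limits the number affected. It does not close the gap. Delay cannot cover urgent cases such as food impaction. Carry-forward is a sensitivity analysis only and may use a score from before or around rescue. The failure/success analysis is worded for patients lost to follow-up, which a rescued patient who exits is not, and it states no value for a continuous EEsAI change.

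Three stronger readings are tempting but not supported:
- *Everyone who stops drug is lost to month 3.* Section 7.1 does not say so, the early termination footnote in 1.3 concerns patients who exit the study, and section 7.2 tells sites to reschedule missed visits and counsel patients on the visit schedule. The clear gap is rescue with exit; off-drug follow-up is ambiguous.
- *The 20% dropout allowance gives the number excluded.* It covers any cause at any time. A patient who leaves after month 3 with both assessments done stays in the primary set. No document gives an exit rate before month 3.
- *The exclusion favours mepolizumab.* The documents give no exit rates by arm and no outcomes after exit, and step 5 shows that the sign can change.

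**Conclusion.** The point holds for rescue before month 3: protocol-defined failures leave the primary ANCOVA because no month-3 EEsAI is requested and the analysis set requires both 3-month assessments. For patients who stop drug without rescue, the finding is ambiguity that sites may resolve differently.

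The bias is of unknown size and direction. The fall from 17 to 15.3 or 13.6 rests on equal exits of 10% or 20%, all before month 3, and no drug effect among exiters. These are assumptions, not estimates, and the gap is nil if exiters respond as completers do. This should be changed because it touches the primary endpoint and the remedy is cheap. It does not by itself invalidate the trial. Confidence is medium.

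**What to change.** Leave the treatment, rescue and safety rules unchanged.

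1. In 6.5.1 and 7.1, state that consenting dosed patients who stop drug or are rescued before month 3 are asked for one EEsAI at the month-3 date, in clinic or by secure survey link.
2. In 9.3, let any dosed patient with a month-3 EEsAI enter the EEsAI analysis, whether or not endoscopy was done.
3. Keep rescued patients in the primary comparison under a stated rule: either the observed month-3 score, or a pre-specified failure value such as the pre-rescue score or no change from baseline. Count them as non-responders for remission and response, and report the other handling as a sensitivity analysis. The rescue data already required by 6.5.1 identify them. Leaving post-rescue scores out with nothing in their place would remove the same patients again.

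**Cost.** One questionnaire per consenting patient who stops or is rescued early, and wording in three sections. A remote EEsAI needs some set-up: section 8.2.1 sends only the SDI electronically, though section 7.2 already foresees emailed survey links. Patients who withdraw consent or are lost cannot be recovered this way.

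**Downside.** The estimated effect may be smaller. In the no-effect case of step 6, power is about 0.86 to 0.90 at 10% exits and 0.73 to 0.82 at 20%, against 0.90 planned. Observed post-rescue scores may reflect steroids or dilation, which is why the choice of rule in item 3 should be made and stated in advance.

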7.2 LOST TO FOLLOW-UP

A participant will be considered lost to follow-up if he or she fails to return for a scheduled study visit and is unable to be contacted by the study site staff.

The following actions must be taken if a participant fails to return to the clinic for a required study visit:

- The site will attempt to contact the participant and reschedule the missed visit at the earliest possible time and counsel the participant on the importance of maintaining the assigned visit schedule and ascertain if the participant wishes to and/or should continue in the study.
- Before a participant is deemed lost to follow-up, the site-investigator or designee will make every effort to regain contact with the participant (where possible, 3 telephone calls and/or email contacts, if necessary, a certified letter to the participant's last known mailing address or local equivalent methods). These contact attempts should be documented in the participant's medical record or study file.
- Should the participant continue to be unreachable, he or she will be considered to have withdrawn from the study with a primary reason of lost to follow-up.

To assist with retention, study staff may contact subjects via email if the participant provided an email address at the time of consent. The email will not contain identifying or health related information, rather will request that the participant get in contact with us to complete required study procedures. Subjects may also receive emails directly from the data management system (REDCap) with links to their secure survey.

8 STUDY ASSESSMENTS AND PROCEDURES

8.1 SCREENING AND BASELINE

During screening/baseline, the following assessments will be completed. Not all are used to determine eligibility. Baseline symptoms are gathered during the screening visit and used as baseline measurements for this study.

1. Informed consent
2. Demographics
3. Medical history
4. EGD with biopsy and EoE Endoscopic Reference Score (EREFs)*
5. EEsAI*
6. Dysphagia Symptom Screening Questionnaire*
7. Patient Global EoE Assessment*
8. VAS (Visual Analog Scale) Assessment; if applicable for subjects with known allergic diseases
9. CBC with differential*
10. Serum/anti-IL 5 antibodies*
11. Physical exam*
12. Vital signs*
13. Urine pregnancy test*
14. Concomitant medication review
15. Straumann Dysphagia Index (SDI)
16. Adverse event review and evaluation
17. Completion of CRFs

*If eligible, then these assessments performed during the screening phase will also be used for baseline and do not need to be repeated at randomization.

All screening and baseline assessments should be completed prior to and within 49 days of randomization.

8.1.1 SYMPTOM ASSESSMENT FOR ELIGIBILITY

Symptom assessment for eligibility will occur via completion of both the EEsAI questionnaire and a dysphagia questionnaire. These questionnaires should be completed during the screening phase after informed consent is obtained and prior to the screening endoscopy.

8.1.2 QUESTIONNAIRES

The following questionnaires will be completed during screening/baseline and are not used to determine eligibility:

1. Patient Global EoE Assessment
2. VAS (Visual Analog Scale) Assessment
3. Straumann Dysphagia Index (SDI)

8.1.3 SCREENING AND BASELINE ENDOSCOPY WITH BIOPSY AND EREFS

Prior to the screening endoscopy, subjects must be deemed eligible per the EEsAI questionnaire and dysphagia questionnaire. Sites must obtain approval from the lead site prior to completing any screening endoscopies for this study. This is to ensure subjects meet symptom requirements to be eligible for the study.

During the screening endoscopy, esophageal biopsies will be obtained from the following locations:

- Distal esophagus (3-5 cm above the Z-line/squamo-columnar junction)
- Proximal esophagus (~15 cm above the Z line and within 10 cm of the esophageal inlet)

Up to 6 esophageal biopsies will be obtained from each location, focusing on areas of endoscopic abnormalities, if present. Biopsies to determine eligibility will be immediately shipped to a Central Lab for analysis.

Additionally, all children (<18 years of age) will have additional biopsies from the stomach (up to 4: 2 from the antrum and 2 from the gastric body) and duodenum (up to 4) taken to rule out alternative etiologies. Similarly, adults (≥ 18 years of age) with abnormal endoscopic findings or cases where other gastric or small intestinal considerations are clinical possibilities will have biopsies taken from the stomach, duodenum, and/or other targeted areas to rule out alternative etiologies.

Additional details regarding biopsy collection, processing, and shipping instructions can be found in the Manual of Procedures (MOP).

Endoscopic findings will be assessed by each investigator using the EoE Endoscopic Reference Score (EREFS)⁵⁰ in 5 classification categories: fixed rings, exudates, furrows, edema, and stricture.

In addition to obtaining the eosinophil counts required for inclusion in the trial and outcome determination, the esophageal biopsies will be used for evaluation of potential diagnostic and pharmacodynamic markers using appropriate laboratory methodology, including but not limited to other histopathologic findings, immunohistochemistry, and transcript profiling. Samples may also be used for future unspecified studies.

If deemed eligible, then biopsies and EoE Endoscopic Reference Score (EREFS) from the screening EGD will also be used as baseline. For this study, baseline symptoms gathered during the screening visit are used as baseline measurements.

8.1.4 SAMPLE COLLECTION

During the screening phase, complete blood count (CBC) with differential will be obtained to determine the baseline peripheral blood absolute eosinophil count.

Screening CBC with differential will be analyzed by local laboratories and results entered into the electronic data capture system. Subsequent CBC with differential will be sent to a Central Lab for analysis and sites will be blinded to results unless abnormal. Blood samples should be obtained on the same day as the EGD.

In addition, on the day of the screening/baseline EGD, a serum sample will be obtained for anti-IL 5 as a baseline measure. Baseline symptoms are gathered during the screening visit and used as baseline measurements. Serum will be sent to the lead site for processing and storage.

Additional details regarding sample collection, processing, and shipping instructions can be found in the MOP.

8.2 RANDOMIZATION VISIT

During the randomization visit, the following will be completed:

- 1) Confirm eligibility based on screening assessments
- 2) Vital Signs
- 3) Urine pregnancy test
- 4) Concomitant medication review
- 5) Randomization
- 6) Administration of study intervention (see section 6 for details)
- 7) Adverse event review and evaluation
- 8) 48-hour adverse event review and evaluation
- 9) Straumann Dysphagia Index (SDI)*
- 10) Completion of CRFs

8.2.1 STRAUMANN DYSPHAGIA INDEX (SDI)

*The Straumann Dysphagia Index (SDI) will be dispensed during the randomization visit and completed weekly between Month 0 - Month 6. The SDI will be sent electronically for participants who have provided an email address at the time of consent between Month 0 visit and Month 6 visit. SDI should be completed during the visit at Screening and Baseline, Month 6, Month 8, and Early Termination (if applicable). Additional details regarding SDI completion can be found in the MOP.

8.3 VISIT MONTHS 1, 2, 4, AND 5

During visit months 1, 2, 4, and 5, the following will be completed:

- 1) EEsAI
- 2) CBC with differential
- 3) Vital signs
- 4) Urine pregnancy test
- 5) Concomitant medication review
- 6) Administration of study intervention (see section 6 for details)
- 7) Adverse event review and evaluation
- 8) 48-hour adverse event review and evaluation
- 9) Weekly Straumann Dysphagia Index (SDI)
- 10) Completion of CRFs

8.3.1 SAMPLE COLLECTION

CBC with differential will be sent to a Central Lab for analysis and sites will be blinded to results unless abnormal. Blood samples should be obtained on the same day as the EGD for the screening visit and visit months 3, 6, and early termination.

Additional details regarding sample collection, processing, and shipping instructions can be found in the MOP.

8.4 VISIT MONTHS 3, 6 AND EARLY TERMINATION

During visit months 3, 6, and early termination the following will be completed:

- 1) Endoscopy with biopsy and EoE Endoscopic Reference Score (EREFS)
- 2) EEsAI
- 3) Patient Global EoE Assessment
- 4) Patient Global Impression of Change (PGIC)
- 5) Patient Global Impression of Severity (PGIS)
- 6) VAS (Visual Analog Scale) Assessment; if applicable for subjects with known allergic diseases
- 7) CBC with differential
- 8) Serum/anti-IL 5 antibodies
- 9) Vital signs
- 10) Physical Exam
- 11) Urine pregnancy test
- 12) Concomitant medication review
- 13) Administration of study intervention (see section 6 for details, 3-month visit only)***
- 14) Adverse event review and evaluation
- 15) 48-hour adverse event review and evaluation (3-month visit only)***
- 16) Straumann Dysphagia Index (SDI)
- 17) Completion of CRFs

*** No study intervention is given at the month 6 visit or early termination visit, therefore no 48-hour phone call is required for these visits.

